3.1.2. Endpoints

Primary Endpoint:

Patient Reported Quality of life related to Radiation Induced Nausea and Vomiting (RINV) as scored by the Functional Living Index – Emesis (FLIE) at day 5 post RT start.

Secondary Endpoints

Primary efficacy outcome

- Control of RINV measured by a daily patient diary (day 1-5)

Secondary Patient Reported Outcome Measures (PROMs)

- Pain flare measured by the Brief Pain Inventory (BPI)
- Diary of medication use (specifically anti-emetics)
- PRO-CTCAE T11 – L5 & Pelvis:
 - Decreased appetite
 - Nausea
 - Vomiting
 - Diarrhea
 - Radiation skin reaction
 - Pain flare
 - Fatigue
- Pain response assessed by the Brief Pain Inventory.
- Proportion of patients who receive treatment within 1 day, 2 days, 3 days, 4 days, 5 days, or more than 5 days,
- Toxicity assessed at baseline and follow-up
- Quality of Life: single item from EORTC QLQ C-15 PAL: How would you rate your overall quality of life during the past week
- Performance status: as reported by patient with PRO-ECOG
- Cost effectiveness of SUPR vs. VMAT assessed by EQ-5D-5L

3.2. Entry Procedures

PRE-TREATMENT ASSESSMENT

- ECOG status
- Eligibility according to inclusion and exclusion criteria
- Patient Reported Outcomes
 - Brief Pain Inventory
 - Functional Living Index – Emesis
 - EQ-5D-5L

Entry Procedures

All randomizations will be done using a computer-generated randomization scheme.

All eligible patients enrolled in the study by the participating treatment centre will be assigned a study number, which must be used on all documentation.

The following information will be required:

- Trial code (where applicable)
- Name of investigator under whose name the patient will be randomized
- Informed consent, version date, date signed by patient, name of person conducting consent discussion and date signed by the person who conducted the consent from discussion
- Confirmation that the patient meets the eligibility requirements in Section 4.0 (as per completed Subject Registration Form)

Stratification factors

All metastases lying at least partly within T11-L5 or the pelvis will be treated according to randomization technique, and should receive the same dose (either 8 Gy in 1 fraction or 20 Gy in 5 fractions), chosen pre-randomization. All other bone metastases that need to be treated can be treated with either 20 Gy in 5 fractions or 8 Gy in 1 fraction, can be treated at the same time. Technique for these lesions can be chosen by RO or centre discretion. The total number of fields that can be treated synchronously is 3, and included both eligible and ineligible fields. If additional bone metastases are symptomatic, they can be treated at a later time, no sooner than 4 weeks from the end of radiotherapy on trial.

A description of the measures taken to minimize avoid bias including:

a. Randomization (simple/restricted/blocked/stratified)

Simple randomization with stratification will be used to randomly assign patients to either Arm 1 or Arm 2 in a 1:1 ratio using a computer-generated randomization scheme known only to the trial statistician.

b. Blinded/Unblinded

It is not ethically or practically feasible to use double- or single-blinding given the nature of the treatments under investigation. Patients will need to consent to participate in the trial, and treating clinicians and staff will be aware of which patients have been assigned to SUPR versus VMAT. Thus, an open-label randomized controlled study design will be used; however, during interim and final analyses, outcomes assessors and data analysts will be blinded to the identity of each treatment arm to ensure unbiased ascertainment of outcomes. The randomization module was developed, reviewed, and approved by the Study Coordinator and Trial Statistician, and randomization scheme is only known to Coordinator and Statistician, per ICH E9.

Protocol number v12.0; 16 Apr 2024

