
This is a randomized, multi-centre, pragmatic phase III study in palliative patients with bone metastases.
 
Randomization will be performed on patient-level, meaning that if a patient is treated for multiple bone metastases in the same course, all will receive the same treatment technique.
	

Protocol number v12.0; 16 Apr 2024

This applies only to bone lesions, as per section 3.2. Any additional lesions to be treated will be at the RO's discretion.

Stratification: 8 Gy/1 vs 20 Gy/5

Radiation Treatment Plan (Arm 1):

Location	Dose (Gy)	Fractions	Frequency
Bone metastasis	8	1	Single fraction
Bone metastasis	20	5	Once daily

Radiation Treatment Plan (Arm 2):

Location	Dose (Gy)	Fractions	Frequency
Bone metastasis	8	1	Single fraction
Bone metastasis	20	5	Once daily

Disease Assessment:

- Patient Reported Quality of life related to RINV as scored by the Functional Living Index – Emesis (FLIE)
- Control of RINV as measured by a daily patient diary
- Patient reported pain response as measured by the Brief Pain Inventory (BPI)
- Patient reported use of medications as measured by patient diary
- Patient reported fatigue, nausea, vomiting as measured by the PRO-CTCAE
- Patient reported quality of life as measured by EORTC QLQ C-15 PAL
- Patient reported functional status as measured by PRO-ECOG
- Economic analysis as measured by EQ-5D-5L

Study Population

Patients with a clinical diagnosis of bone metastases, meeting all inclusion and exclusion eligibility criteria.

Study Objective(s):

Primary Objective

The primary objective is to compare patient-reported Quality of Life related to Radiation Induced Nausea and Vomiting (RINV) between standard palliative radiotherapy and VMAT.

Secondary Objective:

To assess rate of complete control of RINV, compare patient reported toxicity, and evaluate pain response. However, we hypothesize that there will be no difference in pain response between the two arms, because they are receiving the same dose.

Number of Subjects/Sample Size Calculations

250 subjects will be accrued

Planned Study Period:

7 Years

Inclusion Criteria:

Subjects must meet all of the following criteria to be eligible for participation in this study:

- Age 18 or older
- Able to provide informed consent
- Clinical diagnosis of cancer with bone metastases (biopsy not required)

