2.3. Study Population

Patients with a clinical diagnosis of bone metastases, meeting all inclusion and exclusion eligibility criteria.

3. Trial Design

This is a randomized, multi-centre, pragmatic phase III study in palliative patients with bone metastases. Randomization will be performed on patient-level, meaning that if a patient is treated for multiple bone metastases in the same course, all will receive the same treatment technique. This applies only to bone lesions, as per section 3.2. Any additional lesions to be treated will be at the RO's discretion.

Patients will be stratified by treatment dose of either 8 Gy in a single fraction or 20 Gy in 5 fractions.

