9.2. Planned Subjects Enrolled

The primary outcome is Functional Living Index – Emesis (FLIE) score compared between the two arms at day 5 post start of RT. We expect patients in the SUPR arm to have a mean FLIE score of 36, 5 days post start of RT¹⁷. We anticipate that VMAT will have a much lower RINV impact (i.e. less decline in FLIE) and for the purpose of this study will hypothesize that the FLIE will be approximately 28. The standard deviation used for sample size calculation was 16.

Sample size was calculated with these FLIE scores. With alpha Type I error set at 0.05 and power set at 0.9, with a dropout rate of 30%, we calculated a conservative sample size of 250 patients. This dropout rate of 30% is a conservative number. We will collect patient demographics and if there is an indication that bias is being introduced because of dropout, we will consult with a statistician.

Our most important secondary outcome (primary efficacy outcome) is radiation induced nausea and vomiting (RINV) which occurs in 60% of patients who receive RT to the lower spine or pelvis^{17, 18}. Using the sample size of 250 patients (see above), this study has a power of 0.8 to detect a 25% difference in RINV (from 60% to 35%) with alpha Type I error set at 0.05 and a dropout rate of 20%. As outlined in the table below, if RINV difference is lower, or higher our power will be lower and higher, respectively.

Health-Related Quality of Life (HRQoL) will be measured using the EQ-5D-5L and combined with survival outcomes to explore differences in Quality Adjusted Life Year (QALY) gains or losses between treatments¹⁹.

Approximate sample size required

RINV 60% to 50% 1600

RINV 60% to 40% 400

Protocol number v12.0; 16 Apr 2024

RINV 60% to 35%	250
RINV 60% to 30%	175
RINV 60% to 20%	90

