12.3. Trial Management

The Coordinating Centre for this study will be BC Cancer-Prince George under leadership of [name] as Study Principal Investigator. [name] and the Coordinating Centre will be responsible for trial activities at all participating sites, including international sites. The Coordinating Centre will be responsible for randomization of participants using a randomization module in the REDCap Electronic Data Capture (EDC) system which will be used for trial data collection. In conjunction with trial statistician and Site Principal Investigators, the Coordinating Centre will be responsible for storing and analyzing trial data. Designated Site Principal Investigators will be responsible for reviewing eligibility of participants at their centre. In addition to providing credentials, evidence of regulatory training, and evidence of IRB/REB approval, all sites will receive protocol training and data entry training prior to site initiations.

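### As worded, the dose stratification gives no balance beyond chance and the primary t-test does not use it; adjust the Day 5 FLIE analysis for dose stratum and state the allocation method actually used

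*Combined protocol and SAP*

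**What the plan says.** The synopsis gives the factor as "Stratification: 8 Gy/1 vs 20 Gy/5", and section 3 repeats it: "Patients will be stratified by treatment dose of either 8 Gy in a single fraction or 20 Gy in 5 fractions". Section 3.2 has an item that begins "a. Randomization (simple/restricted/blocked/stratified", which lists simple, restricted, blocked and stratified as separate options. The answer given there is "Simple randomization with stratification will be used to randomly assign patients to either Arm 1 or Arm 2 in a 1:1 ratio". Section 12.3 assigns to the coordinating centre "randomization of participants using a randomization module in the REDCap Electronic Data Capture (EDC) system". Neither place mentions block sizes, permuted blocks or minimisation, and nor does any other section.

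Section 9.1 states that arms are compared by t-tests on average scores, by intention to treat. It has no term for dose. Section 9.2 sizes the trial on one mean per arm and one standard deviation, with no breakdown by dose schedule.

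**The concern.** Stratified randomisation balances a factor only if allocation inside each stratum is restricted, for example by permuted blocks. Section 3.2 names the unrestricted method and stratification together, and the first cancels the effect of the second. The plan therefore claims a design feature that its stated method does not deliver, and the analysis does not make up for it.

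The protocol gives reasons to expect dose schedule to relate to Day 5 FLIE. Section 2.1 associates multiple fractions with more acute toxicity and reserves 20 Gy in 5 for bone metastases with specified complications, so the stratum marks both toxicity risk and type of patient. In the schedule in 4.8, Day 5 is a treatment visit in general but a follow-up visit for single-fraction patients, so the primary assessment falls at a different point relative to treatment in the two strata. If the arms happened to differ in their share of 20 Gy patients, the unadjusted difference would carry part of the schedule effect, and readers would question the result.

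**Working it through.** **Inputs from the documents.** Total N = 250 (synopsis: "250 subjects will be accrued"). From 9.2: means 36 ("We expect patients in the SUPR arm to have a mean FLIE score of 36, 5 days post start of RT") and 28, SD 16, and "With alpha Type I error set at 0.05 and power set at 0.9, with a dropout rate of 30"%. Allocation is 1:1 (3.2). Recruitment runs from 1-Aug-19 to 30-Jun-25 (3.3). The protocol version is dated 16 Apr 2024.

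**Assumption.** The share of patients on 20 Gy is not given. I use 10% to 40% and add 50% as an outer case.

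**The plan's own figure.** n per arm = 2(1.960 + 1.282)² × 16² / 8² = 84.06, so 85 per arm and 170 in total. Dividing by 0.7 for dropout gives 243. The exact t-test needs 86 per arm, and 172 / 0.7 = 246. Both agree with 250 to within 3%, taking alpha as two-sided.

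**Does stratifying a simple list change anything?** With 50 of 250 on 20 Gy, 400,000 simulated allocations gave a chance of 32.8% that the arms differ by at least 5 percentage points in the 20 Gy share, and 4.7% for at least 10 points. These figures were the same for separate simple lists by stratum and for one unstratified list. This is expected, because each patient is an independent 1:1 draw in both schemes.

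**Imbalance in the 20 Gy share under simple allocation (binomial within each stratum)**

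| Assumed 20 Gy share | Patients on 20 Gy | P(at least 5 points) | P(at least 10 points) |
|---|---|---|---|
| 10% | 25 | 19% | 0.8% |
| 20% | 50 | 33% | 4.7% |
| 30% | 75 | 39% | 8.5% |
| 40% | 100 | 42% | 10.6% |
| 50% | 125 | 41% | 11.4% |

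In a stratum of 50, a 30:20 split or worse has probability 0.20. By comparison, permuted blocks of 4 in each of two trial-wide strata would cap the difference in share at 1.6 points, and blocks of 6 at 2.4 points.

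**Arm sizes and power.** The SD of the difference in arm size is √250 = 15.8, and P(difference of 20 or more) = 0.23. With 250 × 0.7 = 175 evaluable patients in equal arms, SE = 16√(2/87.5) = 2.42 and power is 91.1%. If the randomised arms differ by 31 (1.96 × 15.8), about 98.3 and 76.7 are evaluable and power is 90.7%. The loss is 0.4 points.

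**Size in FLIE points (illustration only).** The documents give no FLIE values by schedule. If the strata differed by 8 points, as much as the whole hypothesised treatment effect, a 10-point imbalance in share would shift the comparison by 0.10 × 8 = 0.8 points. If they differed by a full SD of 16, the shift would be 1.6 points. Both are smaller than the SE of 2.42.

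**What re-blocking could still reach.** From 1-Aug-19 to 16 Apr 2024 is 1,720 of the 2,160 recruitment days, or 80%. Assuming uniform accrual, about 50 patients remained. Perfect balance among those 50 would lower P(arm sizes differ by 20 or more) from 0.23 to 0.18. At a 20% share, it would lower P(at least 10 points) from 4.7% to 2.6%.

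**The case against.** The strongest reply is that this rests on one loosely used word. Read technically, simple randomisation with stratification is close to a contradiction, and the sentence answers a template heading. Block sizes are properly kept out of a protocol, so the list in REDCap may well be blocked. That stands: the documents cannot settle what was loaded. A reader might infer that the trial is known to have run on an unblocked list, and the text does not support that. The defect goes beyond an unstated block size, though, because the plan names the unrestricted method. If the list is blocked, the sentence is wrong and still needs correcting.

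A reader might also infer that a chance imbalance biases or invalidates the primary comparison. It does not. Simple randomisation balances in expectation, the unadjusted difference is unbiased, and its standard error already includes variation between schedules. Unrestricted allocation of 250 patients is defensible, and in an open-label trial it is also the least predictable scheme.

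Finally, section 2.1 encourages single-fraction treatment, so a low 20 Gy share is plausible, and at 10% a 10-point imbalance is rare (0.8%). That also stands, and it is why the range begins there.

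**Conclusion.** The point holds in a limited form. On the text as written, the dose stratification has no effect at either stage: allocation is not restricted within strata, and the analysis ignores the stratum. The chance that the arms differ by 10 or more percentage points in the 20 Gy share is about 1% to 11% for assumed shares of 10% to 40%. Validity is not in question, and the power cost is under 1 point.

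The documents do not support a demand to change the allocation method. That change would reach only about the last fifth of accrual and would trade some unpredictability for a small gain. The case for adjusting the analysis is stronger. It covers every patient, uses the factor that the trial already names, and is appropriate whether or not the list turns out to be blocked. The conclusion rests on reading the method in 3.2 literally, on the assumed range for the 20 Gy share and, for remaining accrual, on uniform recruitment.

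**What to change.** 1. **Section 9.1.** Replace the unadjusted t-test for Day 5 FLIE with a linear model containing arm and dose stratum, the stratum being the schedule chosen before randomisation. Report the adjusted difference with its confidence interval. Specify this before any unblinded comparison. It costs one sentence and one model term with two levels, and needs no new data.
2. **Section 3.2.** State the method actually used in the REDCap table. If the list is blocked, name the restriction (permuted blocks within dose stratum, with sizes held outside the protocol) and delete the word simple. If it is not blocked, do not claim balance by dose, and make the synopsis and section 3 agree. It costs one corrected sentence in each place.
3. **Optional.** If the list is unblocked, permuted blocks of randomly varying size could be used for remaining accrual. This needs a new allocation table and a documented mid-trial change of method, and it adds some predictability in an open-label trial. With little accrual left, leaving the table alone is reasonable once item 1 is in place.

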3.3. Study Duration

Trial Activities	Start date	End date
Database setup, CRF Development	31-Dec-18	31-Mar-19
Ethics/Site Approvals and Clinical Trial Registration	31-Dec-18	27-Feb-19
Site Training / Initiations	1-May-19	30-Oct-19
Patient Recruitment	1-Aug-19	30-Jun-25
Patient Follow-up	15-Aug-19	30-Aug-25
Safety Analysis	1-May-21	07-Sept-21
Interim Data Analysis (est)	1-Dec-24	31-Jan-25
Database Lock / Final Analyses	30-Aug-25	1-Oct-25
Knowledge Translation (KT) & Evaluation	1-Oct-25	31-Dec-25

4. Eligibility

This study will be offered to all patients presenting with a clinical diagnosis of bone metastases meeting inclusion and exclusion criteria.

Waivers to eligibility criteria are not permitted.

4.1. Inclusion Criteria

Subjects must meet all of the following criteria to be eligible for participation in this study:

- Age 18 or older
- Able to provide informed consent
- Clinical diagnosis of cancer with bone metastases (biopsy not required)
- Currently being managed with palliative intent RT to 1-3 RT fields for bone metastases, at least one RT field (PTV) must (at least) partly lie within T11-L5 or pelvis.
- ECOG Performance Status 0-3
- Patient has been determined to potentially benefit from 8 Gy or 20 Gy
- Radiation Oncologist is comfortable prescribing 8 Gy in 1 fraction or 20 Gy in 5 fractions RT for bone metastases
- Negative pregnancy test result for women of child-bearing potential
- The baseline assessment must be completed within required timelines, prior to randomization.
- Patients must be accessible for treatment and follow-up. Investigators must assure themselves the patients randomized on this trial will be available for complete documentation of the treatment, adverse events, and follow-up.
- For simplicity of planning, expected GTV should be less than 20 cm based on radiological or clinical evidence
- Patient must be prescribed a 5-HT3 receptor antagonist (e.g. Ondansetron) as antiemetic prophylaxis prior to RT start.
- Patient is able and willing to complete the quality of life questionnaires, and other assessments that are a part of this study, via paper or using REDCap if they provide their email address on the informed consent

4.2. Exclusion Criteria

Subjects are excluded from the study if any of the following criteria apply:

- Serious medical co-morbidities precluding radiotherapy
- Clinical evidence of spinal cord compression
- Spinal cord in treatment field has already received at least >30 Gy EQD2, defined as:
$$EQD_2 = D \times (d + (\alpha/\beta)) / (2 + (\alpha/\beta))$$

D = total dose given in Gy

d = dose per fraction in Gy

α/β = dose at which the linear and quadratic components of cell kill are equal
- Whole brain radiotherapy (WBRT) within 4 weeks of RT start or planned WBRT in the first 4 weeks after last RT
- Solitary plasmacytoma
- Pregnant or lactating women
- Target volume cannot be encompassed by a single VMAT isocentre
- Custom mould room requirements (shells and other immobilization that is standard-of-care is acceptable)
- Greater than two organs-at-risk requiring optimization.
- Patients requiring treatments outside standard clinical hours
- Implanted electronic device within 10 cm of the RT fields
- Prostheses in the axial plane of the target, or within 1 cm of the PTV out-of-plane
- Previous RT that requires an analysis of cumulative dose (i.e. sum plans or EQD2 calculations)
- Oral or IV contrast if the local standard-of-care requires compensation for this in planning.

4.3. Subject Withdrawal Criteria

Subjects may voluntarily discontinue participation in the study at any time.

If a subject is withdrawn from the study, the assessments and evaluations that would have been performed at the Study Completion/Early Termination (see Section 4.8) should be obtained, if the patient is willing. The SUPR-3D Participant Withdrawal form should also be completed in addition to completion of the Study Termination form in REDCap.

Subjects withdrawn or discontinued can be replaced at the discretion of the sponsor-investigator/Study Principal Investigator.

If a subject is removed because of an adverse or serious event, they should remain under medical observation as long as deemed appropriate by the treating physician, and follow recording and reporting requirements listed in Section 8.2.

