9.1. Statistical Methods

Patients will be analyzed in the groups to which they are assigned (intention-to-treat). All analyses will be done using t-tests between the average scores of the two arms.

RINV will be assessed via Functional Living Index – Emesis (FLIE) scores compared between the two arms at baseline and day 5 post start of RT

Health-Related Quality of Life (HRQoL) will be measured using the EQ-5D-5L and combined with survival outcomes to explore differences in Quality Adjusted Life Year (QALY) gains or losses between treatments

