12.1.2. Protocol Deviations

A protocol deviation occurs when the subject, investigator, or Sponsor fails to adhere to significant protocol requirements affecting the inclusion, exclusion, subject safety and primary endpoint criteria. Protocol deviations for this study include, but are not limited to, the following:

- Failure to meet inclusion/exclusion criteria
- Use of a prohibited concomitant medication
- Failure to comply with OAR constraints
- Failure to comply with treatment dose, fractionations, constraints and/or frequency as specified in this protocol
- Failure to conduct study follow-up visits and/or to collect study-related data within the timeframes as specified in this protocol

Failure to comply with Good Clinical Practice (GCP) guidelines will also result in a protocol deviation. The Sponsor will determine if a protocol deviation will result in withdrawal of a subject.

When a protocol deviation occurs, it must be documented on the Protocol Deviation Log in REDCap. The deviation will be discussed with the investigator and a Protocol Deviation Report detailing the deviation may be requested. This form will be signed by a Sponsor representative and the Investigator. A copy of the form will be filed in the site's regulatory binder and in the Sponsor's files. The deviation may also require further reporting to the REB per BC Cancer SOPs

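### Arm-aware withdrawal after randomisation can lose the day-5 FLIE despite the intention-to-treat statement; discretionary replacement neither repairs that loss nor is needed for power

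*Combined protocol and SAP*

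**What the plan says.** **Replacement.** Section 4.3: "Subjects withdrawn or discontinued can be replaced at the discretion of the sponsor-investigator/Study Principal Investigator". No criteria are given, and the sentence is not confined to patients not yet randomised. Section 11.5 counts a patient who cannot be reached as withdrawn, so such patients are replaceable too.

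**Who can withdraw a patient.** Section 11.3 allows withdrawal at the investigator's discretion, for safety and for other reasons that are not listed. Section 12.1.2 adds: "The Sponsor will determine if a protocol deviation will result in withdrawal of a subject". Its list of deviations includes failure to meet organ-at-risk (OAR) constraints and treatment constraints.

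**Who knows the arm.** Section 3.2: "treating clinicians and staff will be aware of which patients have been assigned to SUPR versus VMAT". The blinding that is kept applies at the interim and final analyses, when "outcomes assessors and data analysts will be blinded to the identity of each treatment arm".

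**What is collected after withdrawal.** Section 4.3 asks for the assessments due at completion or early termination, if the patient is willing, and points to Section 4.8. That schedule has no separate early-termination column. Its final visit is four weeks after the last radiotherapy, and day 5 is a visit of its own.

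**Analysis.** Section 9.1: "Patients will be analyzed in the groups to which they are assigned (intention-to-treat" and "All analyses will be done using t-tests between the average scores of the two arms". Section 9.2: "with a dropout rate of 30%, we calculated a conservative sample size of 250 patients". No method is given for a missing day-5 FLIE. Section 9.2 says only that a statistician will be consulted if dropout appears to introduce bias.

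**The concern.** The primary endpoint is one FLIE score taken five days after radiotherapy starts. Intention-to-treat protects the comparison only if that score is obtained from the patients who were randomised. Here people who know the arm can end a patient's participation, and nothing then requires the day-5 score to be sought. A t-test on observed scores omits that patient, whichever group the patient nominally belongs to.

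The loss need not be equal between arms. Coverage, conformity and maximum-dose limits are written only for VMAT (Section 5.1.2). SUPR follows local planning and does not require dosimetry review (Section 5.1.1). One route to sponsor withdrawal therefore falls mainly on VMAT patients. Section 2.1 also expects VMAT patients to wait longer for treatment, which gives more time for loss between randomisation and day 5.

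The replacement sentence adds to the difficulty. It offers a remedy for lost patients that keeps up the count but not the randomised comparison. The plan does not say whether a replaced patient stays in the analysis, whether the added patient is newly randomised or takes the vacated arm, or whether additions count towards 250.

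**Working it through.** **Inputs from Section 9.2:** day-5 FLIE means of 36 (SUPR) and 28 (VMAT), difference 8; SD 16; alpha 0.05, taken as two-sided because sidedness is not stated; power 0.90; dropout 30%; N = 250.

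**1. Reproduce the 250.**
- n per arm = 2 × (1.960 + 1.282)² × (16/8)² = 84.1, rounded up to 85, so 170 evaluable.
- 170/0.7 = 243. The exact t-test needs 86 per arm, or 172 in all, and 172/0.7 = 246.
- Both agree with the stated 250 after rounding up. The dropout allowance is already in it, and the sample size is not in error.

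**2. Power with nobody replaced.**
- 250 × 0.7 = 175 evaluable, 87.5 per arm.
- SE = 16 × √(2/87.5) = 2.42.
- 8/2.42 = 3.31, and 3.31 − 1.96 = 1.35, which gives power of about 0.91 (0.911 by the normal approximation, 0.908 by the t-test).
- This exceeds the stated 0.90, so replacement is not needed at the planned dropout rate.

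**3. How withdrawal loses the primary outcome.** Take a VMAT patient withdrawn on day 3 because the plan failed a constraint.
- Section 12.1.2 permits the withdrawal.
- Section 4.3 asks for the termination assessments. Even if these include a FLIE, as the final visit in Section 4.8 does, it is not the day-5 score.
- Section 9.1 keeps the patient in the VMAT group, but there is no score for the t-test to use.
- Section 4.3 allows another patient to be enrolled. The missing score stays missing.

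**4. Illustration of informative withdrawal.** These inputs are assumptions and are not in the documents: no true effect; loss of 35% in VMAT and 25% in SUPR; lost patients score 16 points (1 SD) worse than retained patients in the same arm.
- The mean of all patients in an arm equals the retained mean + 16 × the fraction lost.
- Spurious advantage to VMAT = 16 × (0.35 − 0.25) = 1.6 points, and 1.6/8 = 20% of the hypothesised difference.
- 1.6/2.42 = 0.66. Two-sided rejection = P(Z > 1.96 − 0.66) + P(Z < −1.96 − 0.66) ≈ 0.097 + 0.004 = 0.101, against a nominal 0.05.

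A simulation with different assumptions (125 per arm, 30% lost in each arm, at random in SUPR but correlated with worse FLIE in VMAT) gave:

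| Correlation | Spurious VMAT benefit (points) | Type I error |
|---|---|---|
| 0.1 | 0.8 | 6% |
| 0.2 | 1.6 | 10% |
| 0.3 | 2.3 | 16% |
| 0.5 | 4.0 | 39% |

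**5. What replacement does to this.** The shift in step 4 depends on the fractions lost and on how different the lost patients are. The number randomised does not enter. Added patients who are subject to the same loss leave the shift where it was.

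**The case against.** The strongest case on the other side is that replacement is harmless. It can mean randomising one more patient to protect the evaluable number while the original patient stays in the intention-to-treat set. Section 9.1 makes no exception for replaced patients, and no section drops them or assigns a newcomer to the vacated arm. This stands. A reader might infer that replacement in itself contradicts intention-to-treat; the documents do not support that.

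It can also be said that the bias figures belong to missing data, since they would be the same if nobody were replaced and deleting the sentence alone would not change them. This also stands, and it is why they are offered only as an illustration of withdrawal.

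The OAR limits are recommendations that the radiation oncologist may adjust, the deviation list includes many items that apply to both arms, and nothing says that a breach must lead to withdrawal. That weakens any prediction of unequal removal. It does not remove the route, because the coverage, conformity and maximum-dose limits are headed as required and apply only to VMAT.

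There are partial safeguards: telephone follow-up when a visit is not completed (Section 5.5), recorded reasons for discontinuation (Section 11.3), analysts blinded to arm, and justification of departures from the statistical plan (Section 9.3). A patient withdrawn after day 5 may already have given the primary score. None of these governs who is withdrawn, or requires a day-5 FLIE from a patient withdrawn before then.

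Finally, the word subjects in Section 4.3 could cover people who have consented but are not yet randomised. The proposed wording keeps replacement for exactly that case.

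**Conclusion.** The concern holds for arm-aware withdrawal of randomised patients before day 5, with no requirement to obtain the primary outcome afterwards. Discretionary replacement leaves that gap open and is unnecessary for power, which is about 0.91 with 175 evaluable of 250.

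How large the effect would be in this trial cannot be derived from the documents. The 1.6-point shift and the rejection rate of about 0.10 rest wholly on the assumed loss rates and the assumed 1 SD difference, and the simulated range of 6% to 39% rests on assumed correlations. They show that moderate informative withdrawal would matter against a planned difference of 8. They do not show that it occurs.

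Two further inferences should be resisted. A reader might conclude that the randomised comparison is already undone, but the text permits selective removal without showing any. A reader might also conclude that enrolment well beyond 250 is intended, but the protocol summary gives 250 and no section plans for more.

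**What to change.** Amend Sections 4.3, 9.1, 11.3 and 12.1.2 so that they agree:

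1. Delete the replacement sentence, or limit it to subjects withdrawn before randomisation.
2. State that a protocol deviation, or stopping treatment, does not remove a randomised patient from follow-up or from the intention-to-treat analysis.
3. State that the day-5 FLIE is still sought from withdrawn patients who are willing, in addition to the termination assessments.
4. State that the total randomised is fixed at 250.

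The cost is a few sentences in an amendment. No patients are added, and the only data collection involved is a questionnaire already scheduled for every patient. Statements 2 and 3 do the main work; deleting the replacement sentence alone would leave the loss of day-5 scores as it is.
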